5.10.3 Dose Modification for Neurosensory Toxicity

Neurosensory toxicity with these regimens is known to be a consequence of the oxaliplatin. Therefore reduction in this drug is the most important adjustment to make. The table below gives recommendations but is not meant to be prescriptive and dose adjustments according to local protocol may be followed as long as the dose given is carefully annotated in the CRF.

Regimen	Grade 1, or 2 (if Grade 2 persisting ≤7 days)	Grade 2 persisting >7 days	Grade 3	Grade 4
5-FU and Oxaliplatin	Full dose oxaliplatin	Reduce oxaliplatin dose by 25%	Discontinue oxaliplatin	Discontinue oxaliplatin
Capecitabine and Oxaliplatin	Full dose oxaliplatin	Reduce oxaliplatin dose by 25%	Discontinue oxaliplatin	Discontinue oxaliplatin

Acute dysasthesia of the larynx may be mitigated by slowing the rate of infusion of oxaliplatin.

If repeat events of neurosensory toxicity occur; local practice should be followed in terms of any dose reductions applied, with the management of the toxicities being fully documented in the patient's medical records.

5.10.4 Dose Modification for Diarrhoea

Diarrhoea with these regimens is a known consequence of 5-FU and capecitabine. Therefore a dose reduction in these drugs is the most important adjustment to make. The table below gives recommendations and dose adjustments according to local protocol may be followed as long as the dose given is carefully annotated in the CRF.

	Grade 2	Grade 3	Grade 4
	Withhold 5-FU/capecitabine	Withhold 5-FU/capecitabine	Discontinue all
1 st	treatment until recovered to	treatment until recovered to	chemotherapy
occurrence	grade 0-1. Restart at full	grade 0-1. Restart with a	or if physician
	dose	25% dose reduction	deems it in

Version 6: 16th July 2021 Page 45 of 87

			patient's best
			interest
			interrupt until
			resolved to
			grade 0-1 and
			restart with
			50% 5-
			FU/capecitabine
	Withhold 5-FU/capecitabine	Withhold 5-FU/capecitabine	
2 nd	treatment until recovered to	treatment until recovered to	
occurrence	grade 0-1. Restart at 75%	grade 0-1. Restart at 50%	
	dose	dose	
	Withhold 5-FU/capecitabine		
3 rd	treatment until recovered to	Discontinue all chemotherapy	
occurrence	grade 0-1. Restart at 50%	Discontinue all chemotherapy	
	dose		
4th	Discontinue of all		
occurrence	chemotherapy		

If dose reduction of capecitabine or 5-FU does not result in improved tolerance then consideration should be given to reduction of oxaliplatin dose to 100 mg/m^2 on Capecitabine/Oxaliplatin regimen or 75 mg/m^2 on 5-FU/Oxaliplatin regimen.

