5.3.2 Examples of permitted Combination Fluoropyrimidine Regimens

5.3.2.1 Intravenous Combination Fluoropyrimidine Regimens

Oxaliplatin 85mg/m² IV in Glucose 5% (volume as determined by dose) over 2 hours D1 Folinic Acid 350mg IV in 250ml Glucose 5% over 2 hours concurrently with Oxaliplatin D1. Fluorouracil 400mg/m² IV in 100ml Sodium Chloride 0.9% over 10 minutes (or as an IV bolus) D1 Fluorouracil 2400mg/m² IV in 1000ml Sodium Chloride 0.9% (or via central/PICC line) over 46 or 48 hours D1

Repeat every **TWO** weeks.

For patients with **partial DPD deficiency**:

Oxaliplatin 85mg/m² IV in Glucose 5% (volume as determined by dose) over 2 hours D1 Folinic Acid 350mg IV in 250ml Glucose 5% over 2 hours concurrently with Oxaliplatin D1. Fluorouracil 200mg/m² IV in 100ml Sodium Chloride 0.9% over 10 minutes (or as an IV bolus) D1 Fluorouracil 1200mg/m² IV in 1000ml Sodium Chloride 0.9% (or via central/PICC line) over 46 or 48 hours D1

Repeat every **TWO** weeks.

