5.3.2.2 Oral Combination Fluoropyrimidine Regimens

Oxaliplatin 130mg/m^2 IV in Glucose 5% (volume as determined by dose) over 2 hours Day 1 Capecitabine 1000mg/m^2 PO twice daily for 14 days starting on day 1 Repeat every **THREE** weeks.

For patients with **partial DPD deficiency**:

Oxaliplatin 130mg/m^2 IV in Glucose 5% (volume as determined by dose) over 2 hours Day 1 Capecitabine 500mg/m^2 PO twice daily for 14 days starting on day 1 Repeat every **THREE** weeks.

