Fluoropyrimidine Regimens

5-FU dose should be modified as per standard local policy.

Combination Fluoropyrimidine Regimens

5-FU and Oxaliplatin treatment

If > 1 delay, or 1 delay of ≥ 2 weeks occurs, maintain oxaliplatin and infusional 5-FU doses, but omit bolus 5-FU and continue without bolus 5-FU for subsequent doses.

If further delay(s) for myelotoxicity occur despite omitting bolus 5-FU, reduce the oxaliplatin and infusional 5-FU doses by 25%. Further dose reductions can be made at the discretion of the local Investigator.

Following first cycle of chemotherapy

If on the day the second, or subsequent cycle, is due neutrophils <1.0 and/or platelets are between 50 and 75,, reduce doses for subsequent courses by 25% (and omit bolus 5-FU from OxMdG regimen).

If on the day the second, or subsequent cycle, is due neutrophils \leq 0.5 and/or platelets \leq 50, Investigators may at their discretion reduce doses for subsequent courses by 50% (and omit bolus 5-FU from OxMdG regimen). A 25% dose reduction with G-CSF would be an acceptable alternative.

If delay \geq 4 weeks patient will no longer be considered to be on protocol treatment, however the patient will continue to be followed up as per protocol.

G-CSF management of neutropenia will be at the discretion of the local Investigator.

Use of granulocyte colony stimulating factor (G-CSF) is permitted at the discretion of the investigator in this potentially curative situation and in keeping with ASCO or other appropriate institutional or

Version 6: 16th July 2021 Page 44 of 87

national guidelines. As with all concomitant medication, its use (including dosage, duration and indication) should be accurately documented.

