5.10.5 Dose Modifications for other reasons

Respiratory Toxicity

As with other platinum drugs, rare cases of acute interstitial lung disease or lung fibrosis have been reported with oxaliplatin. In the case of unexplained respiratory symptoms or signs, oxaliplatin should be discontinued until further pulmonary investigations exclude an interstitial lung disease.

Stomatitis

Routine mouthcare is recommended. If mouth ulcers occur despite this, dose reduce capecitabine or 5-FU as per table for diarrhoea.

Hand-foot Syndrome (HFS)

Treat symptomatically – e.g. Pyridoxine 50 mgs tds by mouth can be used as per Investigator discretion; or a topical corticosteroid may help. If HFS is still a problem, reduce the dose of capecitabine or 5-FU as per table for diarrhoea.

Some patients (approximately 15%) develop acute hypersensitivity to oxaliplatin. During drug administration, the patient may develop rash, fever, swollen mouth or tongue, hypo- or hypertension and other signs/symptoms of hypersensitivity. This rarely develops to full-blown anaphylaxis, even with repeated treatment. If hypersensitivity does occur a desensitisation protocol as per local practice can be followed and the dose of subsequent cycles be given over a longer time period.

If severe hypersensitivity occurs, discontinue the infusion and treat with IV corticosteroid and antihistamine, as per local practice. After full recovery, the patient may continue with folinic acid and 5-FU or capecitabine.

Oxaliplatin induced laryngeal spasm

If a patient develops laryngeal spasm with no other symptoms of allergic reaction then treatment should be as per investigators discretion and patient should continue on study treatment.

Abnormal Liver Function Tests

In cases of abnormal liver function test results or portal hypertension, which does not obviously result from liver metastases, very rare cases of drug induced hepatic vascular disorders should be considered. Incidences of abnormal liver function tests thought to be attributable to oxaliplatin should be managed as per local practice and documented in the CRF.

Specific Management of Patients taking Capecitabine

Patients allocated Capecitabine must be properly educated in the management of their home-based oral chemotherapy and need to be given rigorous advice with respect to contacting the hospital as soon as toxicities ensue.

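### The dose levels in the diarrhoea section are not reconciled with the reductions in the other toxicity sections, and read literally some would raise a dose already cut

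*Protocol*

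**What the plan says.** **Starting doses.** Among the examples of permitted combinations, section 5.3.2.2 (with capecitabine) has "Oxaliplatin 130mg/m^2 IV in Glucose 5% (volume as determined by dose) over 2 hours Day 1" and section 5.3.2.1 (with 5-FU) has "Oxaliplatin 85mg/m² IV in Glucose 5% (volume as determined by dose) over 2 hours D1".

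**Percentage reductions of oxaliplatin.**
- Section 5.10.3, for grade 2 neurosensory toxicity lasting more than seven days on either combination: "Reduce oxaliplatin dose by 25" per cent.
- Section 5.10.2, 5-FU combination, when delays recur after the bolus has been dropped: "reduce the oxaliplatin and infusional 5-FU doses by 25" per cent.
- Section 5.10.2, capecitabine combination: both drugs are cut by 25% after repeated or long delays. The lower dose is then kept in later cycles, with an exception for further toxicity.
- Section 5.10.2, lower blood counts: a 50% cut on the three-weekly schedule, and a 50% cut at the investigator's discretion on the two-weekly schedule. A 25% cut with G-CSF is an accepted alternative on both.

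**Diarrhoea.** The table in section 5.10.4 gives fluoropyrimidine restart entries by grade and occurrence. The first grade 2 cell ends "grade 0-1. Restart at full" dose. The first grade 3 cell is a 25% reduction. Later cells give 75% or 50% dose, and the grade 4 cell allows a restart at 50%. Below the table, if lowering the fluoropyrimidine does not help, "consideration should be given to reduction of oxaliplatin dose to 100 mg/m^2 on Capecitabine/Oxaliplatin regimen" or "75 mg/m^2 on 5-FU/Oxaliplatin regimen".

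**Reuse of the table.** For hand-foot syndrome that remains a problem, section 5.10.5 says to "reduce the dose of capecitabine or 5-FU as per table for diarrhoea". Stomatitis is sent to the same table.

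**The concern.** Sections 5.10.2 and 5.10.3 move a dose down by a fraction. Section 5.10.4 moves oxaliplatin to a fixed level, and it places the fluoropyrimidine at a mixture of steps and levels. It does not say what happens when the patient has already been reduced for another toxicity. If the stated level lies above the dose in use, an entry meant as a reduction points upwards, in a patient who is accumulating toxicity.

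Two sites could also reach different doses from the same cell. That bears on tolerability, and on the worst-grade toxicity comparison that section 7.3.3 plans for the Oxaliplatin question.

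**Working it through.** **1. Oxaliplatin.** The levels of 100 and 75 mg/m² are stated, not derived, so there is no calculation in the protocol to reproduce. The check compares them with what the protocol's own percentage cuts give at the example starting doses.

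Dose after a cut = starting dose × (1 − cut). Change = named level ÷ dose after the cut − 1.

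| Regimen | Start (mg/m²) | Cut already made | Dose in use (mg/m²) | Level in 5.10.4 (mg/m²) | Change |
|---|---|---|---|---|---|
| With capecitabine | 130 | none | 130 | 100 | −23.1% |
| With capecitabine | 130 | 25% | 130 × 0.75 = 97.5 | 100 | +2.5 (+2.6%) |
| With capecitabine | 130 | 50% | 130 × 0.50 = 65 | 100 | +35 (+53.8%) |
| With 5-FU | 85 | none | 85 | 75 | −11.8% |
| With 5-FU | 85 | 25% | 85 × 0.75 = 63.75 | 75 | +11.25 (+17.6%) |
| With 5-FU | 85 | 50% | 85 × 0.50 = 42.5 | 75 | +32.5 (+76.5%) |

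The levels are true reductions only from the full starting dose. After a 25% or 50% cut under the other sections, both lie above the dose in use.

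**2. Fluoropyrimidine.** The table leaves two things open: whether a percentage refers to the original or the current dose, and whether occurrences are counted within each grade or overall. Taking percentages of the original dose:

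| Sequence | Dose before the last event | Counted per grade | Counted overall |
|---|---|---|---|
| 25% haematological cut, then first diarrhoea episode, grade 2 | 75% | full dose: 100 ÷ 75, +33.3% | same cell, +33.3% |
| First grade 3, then grade 2 | 75% | full dose, +33.3% | second occurrence, 75%: no change |
| Grade 4 restarted at 50%, then grade 2 | 50% | full dose: 100 ÷ 50, +100% | second occurrence, 75%: 75 ÷ 50, +50% |

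The first sequence does not depend on how episodes are counted. It sits against section 5.10.2, which keeps the capecitabine combination at the lower dose in later cycles.

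If percentages are of the current dose, none of these rises occurs, but the results differ in another way. Two grade 3 episodes then lead to 0.75 × 0.50 = 37.5% of the original dose, against 50% on the other reading.

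**3. Stomatitis and hand-foot syndrome.** Section 5.10.5 tells the investigator to lower the dose by the diarrhoea table. The first grade 2 cell of that table contains no lowering, so instruction and table do not match there.

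**The case against.** The strongest reply is that nothing here orders an increase. The oxaliplatin sentence is optional and its action is a reduction. A patient at 97.5 or 63.75 mg/m² cannot be reduced to 100 or 75, so a careful investigator would treat the sentence as not applicable. Section 5.10 places dose changes under institutional practice (and the SmPC for capecitabine). Section 5.10.1 leaves combinations of toxicities that are not covered in detail to the investigator. Sections 5.10.2, 5.10.3 and 5.10.4 each allow local practice. The starting doses are examples, and the 2.5 mg/m² gap on the capecitabine regimen is small enough for permitted dose banding to absorb. All of this stands, and it limits the point to an unreconciled recommendation. It does not remove it: freedom to depart from guidance does not make the guidance consistent.

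A reader might infer more, and the documents do not support it:
- **That the table re-escalates patients as written.** It can do so only if read literally and against the original dose.
- **That a grade 2 episode after a grade 3 episode brings a 33% increase.** That needs counting per grade as well. With occurrences counted overall, the cell gives 75% and the dose does not change.
- **That section 5.10.2 forbids any return to a higher dose.** It is a guideline, and its statement about staying at the lower dose covers only the capecitabine combination and excepts further toxicity. Diarrhoea could be argued to fall under that exception.
- **That the unequal depths of the oxaliplatin step (23.1% and 11.8%) are an error.** They belong to two different regimens and do not contradict each other.

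**Conclusion.** The point holds as an internal inconsistency in advisory dosing text.

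- **Oxaliplatin.** At the protocol's example starting doses, the levels in section 5.10.4 exceed the doses after a 25% cut by 2.6% (with capecitabine) and 17.6% (with 5-FU), and those after a 50% cut by 53.8% and 76.5%. This is plain arithmetic; the size of the gap depends on the institutional starting dose.
- **Fluoropyrimidine.** The defect is a missing reference dose and a missing counting rule. The increases shown are possible results of a literal reading, not established ones.
- **Stomatitis and hand-foot syndrome.** The instruction to lower the dose meets a first grade 2 cell without a reduction.

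No escalation is mandated. The documents do not allow an estimate of how many patients would be affected, or of any effect on the comparison between arms. The text should still be corrected, because it guides dosing in patients with toxicity and the correction is cheap.

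**What to change.** The sponsor should reconcile sections 5.10.2 to 5.10.5 so that:
- the absolute oxaliplatin levels and the percentage steps do not conflict;
- each restart entry names its reference dose, original or current;
- the rule for counting occurrences across grades is stated, and how the table is to be used for stomatitis and hand-foot syndrome is made clear;
- it is clear how the table applies to a patient who is already on a reduced dose.

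The clinical team decides all levels and rules; none is proposed here. The cost is rewording one table, the sentence below it and its cross-references in a protocol amendment, with the approvals that section 11.8 requires. It needs no new procedures and no change to the sample size.

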5.10.5 Dose Modifications for other reasons

Respiratory Toxicity

As with other platinum drugs, rare cases of acute interstitial lung disease or lung fibrosis have been reported with oxaliplatin. In the case of unexplained respiratory symptoms or signs, oxaliplatin should be discontinued until further pulmonary investigations exclude an interstitial lung disease.

Stomatitis

Routine mouthcare is recommended. If mouth ulcers occur despite this, dose reduce capecitabine or 5-FU as per table for diarrhoea.

Hand-foot Syndrome (HFS)

Treat symptomatically – e.g. Pyridoxine 50 mgs tds by mouth can be used as per Investigator discretion; or a topical corticosteroid may help. If HFS is still a problem, reduce the dose of capecitabine or 5-FU as per table for diarrhoea.

Some patients (approximately 15%) develop acute hypersensitivity to oxaliplatin. During drug administration, the patient may develop rash, fever, swollen mouth or tongue, hypo- or hypertension and other signs/symptoms of hypersensitivity. This rarely develops to full-blown anaphylaxis, even with repeated treatment. If hypersensitivity does occur a desensitisation protocol as per local practice can be followed and the dose of subsequent cycles be given over a longer time period.

If severe hypersensitivity occurs, discontinue the infusion and treat with IV corticosteroid and antihistamine, as per local practice. After full recovery, the patient may continue with folinic acid and 5-FU or capecitabine.

Oxaliplatin induced laryngeal spasm

If a patient develops laryngeal spasm with no other symptoms of allergic reaction then treatment should be as per investigators discretion and patient should continue on study treatment.

Abnormal Liver Function Tests

In cases of abnormal liver function test results or portal hypertension, which does not obviously result from liver metastases, very rare cases of drug induced hepatic vascular disorders should be considered. Incidences of abnormal liver function tests thought to be attributable to oxaliplatin should be managed as per local practice and documented in the CRF.

Specific Management of Patients taking Capecitabine

Patients allocated Capecitabine must be properly educated in the management of their home-based oral chemotherapy and need to be given rigorous advice with respect to contacting the hospital as soon as toxicities ensue.

Patients may often be prepared to experience toxicities and may not easily accept the idea of interrupting their treatment for fear this may decrease efficacy. Patients should be re-assured that protocol compliant dose modifications will not compromise the efficacy of their treatment, and must be given clear instructions on when to discontinue capecitabine and who to contact (local Investigator/Research Nurse) at the onset of key toxicities such as nausea/vomiting and diarrhoea.

Cardiotoxicity has been associated with fluoropyrimidine therapy and these adverse reactions may be more common in patients with a prior history of coronary artery disease. Cardiac arrhythmias have been reported in patients receiving capecitabine. Caution must be exercised in patients with history of significant cardiac disease, arrhythmias and angina pectoris (see Capecitabine SmPC for further information). Incidences of cardiotoxicity arising from capecitabine treatment should be managed as per standard local practice and documented in the CRF.

Version 6: 16th July 2021 Page 47 of 87

5.11 Participation in Concurrent Clinical Trials

In general patients should not participate simultaneously in more than one trial, with the following exceptions:-

- Patients will be permitted to take part in observational research at any time whilst participating in this trial
- Patients who have attained the primary trial end-point and are no longer receiving the trial intervention.
- Patients who have progressed can enter a trial for recurrent or metastatic disease

If an exception is considered outwith the above general criteria the PI seeking the exception must seek approval from the CI and Trial Management Group prior to enrolling the patient in the other trial. It is imperative that the Sponsors of both studies also approve co-enrolment within their trial.

5.12 Duration of Trial Participation

5.12.1 Duration of Trial Treatment

Trial treatment will continue for up to 24 weeks (or 26 weeks for certain permitted regimens).

5.12.2 Duration of Trial Follow Up

Patients will be followed up for up to 7 years post randomisation

6 PHARMACOVIGILANCE

Safety assessments will be performed in line with guidance specified in The Medicines for Human Use (Clinical Trials) Regulations 2004 and any subsequent amendments to it. The following definitions and reporting requirements apply to BALLAD UK only.

6.1 Definitions

These definitions apply to all trial participants from the first dose of trial medication.

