2.2 Secondary Objectives

 Assess the toxicity of chemotherapy, the cost-effectiveness of the treatment alternatives and establish a central tissue and data bank for patients with this rare cancer.

Version 6: 16th July 2021 Page 25 of 87

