3.5 Randomisation

For those patients willing to be randomised; the randomisation options depend on the patient group:

Group 1: R0 resected stage I/II/III/IV patients where there is uncertainty of the value of adjuvant chemotherapy

Version 6: 16th July 2021 Page 28 of 87

Patients in this group will be randomised 1:1 to adjuvant chemotherapy or observation. An initial choice must be made by the clinician or patient whether, if allocated to chemotherapy, they will

receive either:

a) 24 weeks of intravenous 5-FU/FA or oral capecitabine

b) 24 weeks of intravenous 5-FU/FA or oral capecitabine + intravenous oxaliplatin

c) Either a or b allocated at random

For all options the fluoropyrimidine choice must be specified prior to randomisation (1:1)

For patients that are going into the observation v chemotherapy randomisation with the clinician's

choice of chemotherapy being used they should be consented and randomised to the study using

patient information sheet A

For patients that are going into the observation v single agent chemo v double agent chemotherapy

randomisation, i.e. will be contributing to both groups, they should be consented and randomised to

the study using patient information sheet B

Group 2: R0 resected stage I/II/III/IV patients where there is certainty of the value of

adjuvant chemotherapy.

Patients in this group will be randomised 1:1 to 24 weeks of fluoropyrimidine based adjuvant

chemotherapy with or without oxaliplatin. The choice of 5-FU/FA or Capecitabine must be specified

prior to randomisation.

For patients that are going into the single agent v double agent chemotherapy randomisation they

should be randomised using patient information sheet C

To register/randomise a patient on the trial, contact the CRUK Glasgow CTU.

Registration/Randomisation to the trial can be performed by either telephone, fax or email using the

following details:

[contact]

[contact]

Email: [contact]

Randomisation service: Monday Thursday 08.30 - 17.00, Friday 08.30 - 16.30. Fax 24 hours.

(Faxes or emails received outside office hours will be dealt with the next working day.)

The patient's eligibility criteria will be checked and, if eligible, a three digit trial number will be allocated

at this point.

Patients will be stratified for:

Version 6: 16th July 2021 Page 29 of 87

- Tumour stage
- Tumour location (jejunum and ileum or duodenum)
- Country
- Choice of preferred fluoropyrimidine (5-FU/FA or Capecitabine)

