4.3.2 Secondary Endpoints

Overall survival: The patient's survival status is determined at each follow-up visit. After the mandated clinic visits survival status data will come from responsible cancer centres, cancer registries and national databases and include long-term passive follow-up data such as that collected through collaboration with the National Cancer Intelligence Network and the Office of National Statistics in the U.K.

Toxicity of chemotherapy: Toxicity will be assessed using CTCAE version 4.0. Only toxicities that are at least grade 2 will be recorded on the CRF

Quality of life: This is assessed using the EORTC QLQ-C30, EORTC QLQ-CR29 v2.1 and EQ-5D scales as per the schedule indicated in section 4.1.5

Health Economics: Assess the cost-effectiveness of 24 weeks adjuvant chemotherapy in comparison to observation alone; and assess the cost-effectiveness of 24 weeks adjuvant 5-FU/Capecitabine monotherapy compared to 5-FU/Capecitabine plus Oxaliplatin. Outcomes will be reported as incremental cost per DFS and incremental cost per QALY.

Establishment of a central tissue bank for patients with SBA – further details on this tissue bank can be found in section 4.2, Translational Research.

Establishment of a central repository of clinic-pathological, epidemiological and molecular profiling data of patients being treated with SBA in this trial.

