6.1.1 Adverse Event (AE)

An adverse event (AE) is any untoward medical occurrence in a subject to whom a medicinal product has been administered, including occurrences which are not necessarily caused by or related to that product.

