7.3.3 Safety Analysis

The worst grade of CTCAE toxicity during the treatment period will be compared between the randomised arms for the Oxaliplatin question.

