7.3.5 Cost Effectiveness

The economic analysis will be undertaken from the perspective of the UK National Health Service (NHS), to assess the cost-effectiveness of adjuvant chemotherapy compared to observation only (Adjuvant question – Group 1) and 5-FU/FA or capecitabine compared to 5-FU/FA or capecitabine plus oxaliplatin (Oxaliplatin question – Group 2). Trial information on resource-use (i.e. treatment delivery, hospital inpatient/outpatient days etc.) will be combined with unit costs to estimate the mean cost per patient in each arm (including treatment costs, costs of managing adverse events and

Version 6: 16th July 2021 Page 58 of 87

costs of managing disease recurrence). Quality of life will be measured using the EQ-5D (16) to determine any difference over the course of the treatment period between trial arms, and beyond the treatment period up to 7 years follow-up. QoL estimates will be combined with DFS and OS and analysed as the area under the curve (AUC) to determine the mean difference in QALYs between the treatment arms, for both research questions. The analysis will be presented separately for the within trial and lifetime periods, in accordance with good practice guidelines and the NICE reference case (17-19).

A multivariate analysis of quality of life and costs, using the occurrence of adverse events and the stage of disease progression as explanatory variables, will be used to inform the lifetime cost-effectiveness model. The lifetime analysis will extrapolate the trial outcomes using a parametric survival model (e.g. weibull, log-logistic, gamma) based on fit to the observed data together with extensive sensitivity analysis following the approach recently recommended by the NICE Decision Support Unit (20,21). The model will be analysed probabilistically to characterise uncertainty in the parameters (22), and estimate confidence limits around the cost and effectiveness outcomes for each of the research questions.

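### CTCAE-graded toxicity cannot be compared between chemotherapy and observation, and section 7.3.3 does not plan the indirect comparison that existing data allow

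*Protocol*

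**What the plan says.** Section 2.2 sets as a secondary objective to "Assess the toxicity of chemotherapy, the cost-effectiveness of the treatment alternatives", and section 4.3.2 makes toxicity an endpoint: "Toxicity will be assessed using CTCAE version 4.0", with grade 2 and above entered on the CRF. Section 3.5 describes Group 1: "Patients in this group will be randomised 1:1 to adjuvant chemotherapy or observation".

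On collection, section 4.1.2 and both chemotherapy schedules require a toxicity assessment at every cycle. The observation schedule has no such row. Section 4.1.3 lists a blood count, biochemistry and quality of life at months 3 and 6, and the schedule table adds a physical assessment covering neuropathy and hearing.

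On definitions, section 6.1 states "These definitions apply to all trial participants from the first dose of trial medication", and section 6.1.1 defines an adverse event as "any untoward medical occurrence in a subject to whom a medicinal product has been administered". Section 6.2.1 nevertheless has participants asked about adverse events at every trial visit. Section 6.4 exempts SAEs unrelated to trial treatment from reporting.

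On analysis, section 7.3.3 says that worst CTCAE grade "will be compared between the randomised arms for the Oxaliplatin question" and mentions no other comparison. Section 7.3.5 plans "A multivariate analysis of quality of life and costs, using the occurrence of adverse events and the stage of disease progression as explanatory variables" to inform the lifetime cost-effectiveness model for both questions.

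**The concern.** The adjuvant question weighs a hoped-for gain in disease-free survival against the harm of 24 weeks of chemotherapy. After small bowel resection some patients will have diarrhoea, fatigue or abnormal bloods without any chemotherapy, and section 6.1.1 counts events whether or not the drug caused them. At grade 2 or above, such background events reach the CRF in the chemotherapy arm. In the observation arm they have no place to be recorded. The trial would then report CTCAE rates on chemotherapy with no concurrent rate to subtract.

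The same gap reaches the economic work. For the adjuvant question, adverse-event occurrence would be recorded in one arm only, so a model that pooled the arms without a term for arm would mix the effect of events with the effect of treatment.

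Sites also face an unclear instruction. Section 6.2.1 reads as covering every participant, while 6.1 and 6.1.1 give no starting point for a patient who is never dosed.

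**Working it through.** The protocol gives no figure to reproduce. The check sets its sections side by side and then asks how far a change would reach.

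**1. What each Group 1 arm provides up to month 6**

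| Item | Chemotherapy | Observation |
|---|---|---|
| CTCAE toxicity check | Every cycle (4.1.2, both schedules) | None (4.1.3, schedule) |
| AE and SAE definitions (6.1, 6.1.1) | Apply from first dose | Never start |
| FBC, U&E, LFTs | Before each cycle | Months 3 and 6 |
| Clinical assessment | Every cycle (schedules) | Months 3 and 6 (schedule) |
| QLQ-C30/CR29 and EQ-5D | About months 3 and 6 | Months 3 and 6 |

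The first two rows rule out a comparison of CTCAE rates. The last three permit an indirect one.

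**2. Whether the times match**

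Months 3 and 6 are about weeks 13 and 26. Day 1 of cycle k falls 2(k − 1) or 3(k − 1) weeks after treatment starts, and the schedule footnote has treatment start within 2 weeks of randomisation. If there are no delays:

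- Bloods nearest month 3: two-weekly cycle 7 at 2 × 6 = 12 weeks, and three-weekly cycle 5 at 3 × 4 = 12 weeks. That is weeks 12–14 from randomisation.
- Last pre-cycle bloods: two-weekly cycle 12 at 2 × 11 = 22 weeks, and three-weekly cycle 8 at 3 × 7 = 21 weeks. That is weeks 21–24 from randomisation.
- First on-treatment questionnaire: two-weekly cycle 6 at 2 × 5 = 10 weeks, and three-weekly cycle 4 at 3 × 3 = 9 weeks. That is weeks 9–12 from randomisation. The second is at cycle 12 or 8, weeks 21–24.

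The arms are therefore aligned to within about 1–5 weeks. Comparing the worst value over all cycles with two observation values would not be like for like, so one value per time point is needed.

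**3. How many patients a UK change reaches**

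The Question 1 recruitment figure in section 7.2 gives 77 patients: UK 10, France 9, Japan 58. The UK share is 10/77 = 13%. Projected final recruitment is 95 to 114, so 18 to 37 more worldwide. If the UK share holds (an assumption), that is 0.13 × 18 ≈ 2 to 0.13 × 37 ≈ 5 more UK patients, of whom about 1–2 would be on observation.

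**4. Illustrative precision**

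The event rates here are assumptions, not protocol figures: 30% with a given grade 2 or higher symptom on chemotherapy and 10–20% on observation. The 95% half-width is 1.96 × √[(p₁(1 − p₁) + p₀(1 − p₀))/n].

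- Pooled, about 105 patients, n = 52 per arm: 1.96 × √(0.30/52) = 0.149 to 1.96 × √(0.37/52) = 0.165, or about 15–17 percentage points. This requires every collaborating trial to collect the data.
- UK alone at present, n = 5 per arm: 1.96 × √(0.30/5) = 0.48 to 1.96 × √(0.37/5) = 0.53, or about 48–53 points.

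**5. The regression in 7.3.5**

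Adverse events vary among chemotherapy patients, so their effect on quality of life and cost can be estimated within that arm or with arm in the model. Section 7.3.5 names two explanatory variables and is silent on arm.

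**The case against.** A reader might infer that the toxicity of chemotherapy cannot be judged against observation at all. The protocol does not support that: laboratory values, a clinical assessment and symptom questionnaires exist in both arms, and section 7.3.4 already plans an AUC analysis of quality of life. What is missing is a CTCAE comparison and any plan to use the shared data as safety evidence.

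A reader might also infer that a stated objective is contradicted. It is not. Sections 2.2 and 4.3.2 speak of chemotherapy toxicity without naming observation as comparator. Attribution is not wholly crude either: events are assessed for causality (6.2.3), and relationship to trial drug is noted in the medical records (6.2.2). In an open-label trial, though, an investigator's attribution does not replace a concurrent control rate.

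The claim that the economic model's adverse-event coefficient is confounded with arm goes further than the text, because 7.3.5 does not say that arm is left out. Within-trial QALYs rest on EQ-5D and survival, and costs on hospital resource use; both are available for observation patients.

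The strongest objection concerns reach. Section 6 governs BALLAD UK only, and the other trials run their own protocols and safety reporting. What they collect on observation is not visible here, so a gap in the pooled data is not shown. This stands, and it limits the value of new CTCAE collection. It does not affect the proposal to analyse data already held, nor the need to reconcile 6.1 with 6.2.1.

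Finally, an analysis plan could add a table for the adjuvant question. It could not add CTCAE grades that the schedule never called for.

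**Conclusion.** The point holds in a limited form. Within BALLAD UK, CTCAE-graded toxicity cannot be compared between chemotherapy and observation, because collection, definitions and planned analysis all leave out the observation arm. The indirect comparison that the shared data permit is not planned in 7.3.3. Sections 6.1 and 6.1.1 fit poorly with 6.2.1 and need reconciling whatever else is done.

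This is a design gap in the benefit–harm assessment of one primary question. The efficacy analysis is unaffected. No factor can be given for how far uncontrolled rates overstate chemotherapy toxicity, since the protocol contains no background rate. The 15–17 point precision above is illustrative and applies only to pooled data. The conclusion on small yield rests on the section 7.2 recruitment figure and on the UK share staying near 13%.

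**What to change.** 1. **Section 7.3.3.** Extend it to the adjuvant question. Compare graded FBC, U&E and LFT values and QLQ-C30/CR29 symptom scores between the Group 1 arms at about 3 and 6 months, using one value per patient per time point: for chemotherapy patients, the pre-cycle result nearest the target date. Report differences with confidence intervals.

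2. **Sections 6.1, 6.1.1 and 6.2.1, and the observation schedule.** Reconcile them by stating that non-serious events of grade 2 or above are recorded on the CRF from randomisation in both Group 1 arms. Add that check to the existing month 3 and 6 observation visits. This can be a recording rule separate from the regulatory definitions, leaving SAE reporting unchanged. Ask the other GLOBAL BALLAD trials to do the same. For patients already past month 6, rely on laboratory and questionnaire data.

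3. **Section 7.3.5.** State that the effect of adverse events on quality of life and cost is estimated with adjustment for arm, or within the chemotherapy arm.

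The cost is a protocol amendment, two short CRF pages per observation patient and one added table. Three limits should be stated in the report. Observation patients are asked less often than patients seen every cycle, so minor events will be missed. Symptom scores are self-reported in an open-label trial. New CTCAE data will be sparse if only the UK changes, leaving the existing laboratory and questionnaire data to carry most of the comparison.
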